2.2. Endpoints

Primary Efficacy Endpoints:

CLUE Overall Quality of Vision

Overall comfort scores will be assessed using the Contact Lens User Experience (CLUE™) questionnaire after approximately 2 weeks of lens wear. CLUE is a validated patient-reported outcomes questionnaire to assess patient-experience attributes of soft, disposable contact lenses (comfort, vision, handling, and packaging) in a contact-lens wearing population in the US, ages 18-65. Derived CLUE™ scores using Item Response Theory (IRT) follow a normal distribution with a population average score of 60 (SD 20), where higher scores indicate a more

Clinical Study Protocol

Johnson & Johnson Vision Care, Inc.

favorable/positive response with a range of 0-120. A 5-point increase in an average CLUE™ score translates into 10% shift in the distribution of scores for population of soft contact lens wearers⁷.

Visual Acuity (logMAR)

Multiple assessments of binocular and monocular visual acuity will be made during the study, but the binocular measurements made after approximately 2 weeks of lens wear using high contrast letters in bright illuminance conditions will be the primary endpoint. At distance (4 meters), VA is assessed using ETDRS Charts; while near (40 cm) and intermediate (64 cm) assessments will be made using reduced Guillon-Poling charts. Visual acuity will be measured using high and low contrast charts in bright illuminance conditions.

Primary Safety Endpoints:

Slit Lamp Findings (SLF)

Slit Lamp Findings (Grade 3 or higher) will be assessed for each subject eye at all study visits (schedule and unscheduled). SLFs will be evaluated and classified using the FDA Grading scale rating from 0 to 4, where Grade 0 represents the absence of findings and 1 to 4 representing successively worse findings (i.e. Grade 1=trace, Grade 2= mile, Grade 3=moderate and Grade 4= severe). The percentage of eyes with Grade 3 or higher slit lamp findings will be analyzed and will include corneal infiltrates.

Unacceptable Lens Fit

Unacceptable lens fit will be assessed at all study visits (scheduled and unscheduled) for each subject eye. Unacceptable fit is a binary response where Y=1 if lens fit is unacceptable and Y=0 otherwise. Unacceptable fit was defined as unacceptable if any one of the following criteria:

- limbal exposure at primary gaze or with extreme eye movement;
- edge lift;
- excessive movement in primary up gaze;

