2.3. Hypotheses

All the following co-primary hypotheses must be satisfied in order to meet the study objectives.

Primary Hypotheses:

1. After approximately 2-weeks of wear, the mean overall quality of vision score of the Test lenses will be statistically better than 40 points for the myope population. This will be recorded by the subject using the CLUE Follow-up Questionnaire.
2. After approximately 2-weeks of wear, the mean overall quality of vision score for the Test lenses will be statistically better than 32 points for the hyperope population. This will be recorded by the subject using the CLUE Follow-up Questionnaire.
3. After approximately 2-weeks of wear, the mean distance, binocular, high luminance, high contrast logMAR visual acuity score of the Test lens will be statistically lower than 0.10 logMAR.
4. After approximately 2-weeks of wear, the mean intermediate, binocular, high luminance, high contrast logMAR visual acuity score of the Test lens will be statistically lower than 0.17 logMAR.
5. After approximately 2-weeks of wear the mean near, binocular, high luminance, high contrast logMAR visual acuity score of the Test lens will be statistically lower than 0.17 logMAR.
6. When wearing the Test lenses, the proportion (%) of eyes with at least one reported clinically significant slit-lamp finding (Grade 3 or 4) during the post-fit period will be significantly lower than 5%.
7. When wearing the Test lenses, the proportion (%) of eyes with an unacceptable fit during the study will be statistically less than 5%.

If all the primary hypotheses are met, the following secondary hypothesis will be tested.

Clinical Study Protocol

Johnson & Johnson Vision Care, Inc.

Secondary Hypothesis:

1. The proportion of subjects who obtain the optimum lens pair in 4 lenses or less will be at least 90% using a 95% level of confidence.

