Johnson & Johnson Vision Care, Inc.

		
Investigator's discretion and based upon their findings on the measured visual acuity and/or over-refraction the investigator may make a modification.
 
Up to two attempts at modification are permitted if necessary, in order to achieve an acceptable distance and near binocular performance for the subject, and to enable them to wear that particular lens type.
 
Follow the fitting guide allowing for at least 10 minutes of settling time between each lens modification attempted.
 
If modifications are required steps 1.21-1.27 will be repeated for each modification.
	
1.29	Post-Fit GSI Product Performance Questionnaire	
The subject will evaluate the vision characteristics, comfort characteristics, handling characteristics, and visual symptoms of the study lenses using the GSI questionnaire.
	
1.30	Distance and Near Exit Visual Acuity	
Distance and near Snellen visual acuity will be measured for each eye with the study contact lenses in place.
 
For near measures use the ETDRS 2000 Series Chart 1 or 2. The acuity will be recorded to the nearest letter OD, OS and OU.
 
Note: The distance visual acuity must be at least 20/30 OU for the lenses to be dispensed.
	
1.31	Dispensing Criteria	
The lenses will be dispensed for 2-4 days.
 
 • Distance Snellen acuity equal to or better than 20/30 OU • Subject must indicate that the vision is acceptable. • Subject must indicate that the comfort of the lenses is acceptable. • Lenses must have an acceptable general lens fit. 	
1.32	Patient Instructions	
Instruct the Subject the following:
 
 • The lenses will be worn on a daily wear basis. 	

Clinical Study Protocol
Johnson & Johnson Vision Care, Inc.

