		
 • OPTI-FREE® Replenish® solution will be used in a rub regime to disinfect and store the lenses each night in the lens case provided. • If determined necessary by the Investigator sterile non-preserved rewetting drops may be dispensed to be used as needed for dryness. • Subjects will be instructed to wear lenses for a minimum of 6 hours a day, every day during the study. • Subjects will be instructed to wear their glasses when not wearing the study lenses. • A patient instruction booklet will be provided. 
Note: In the event a lens is lost or damaged, the subject will return to the investigator site for replacement. As much as reasonably possible, a damaged lens should be returned to the investigational site and then returned to the Sponsor. If lens damage is present, complete the Product Quality Complaint Form. The lens will be stored in labeled vial with sterile saline, and returned to the Sponsor.
	
1.33	Schedule Follow-up	
The subject will be scheduled to return for their follow-up appointment in 3 ± 1 day.
 
Note: To count the follow-up visit as a day of wear the Subject must have worn the study lenses for 6 hours prior to the visit.
	

VISIT 2

The subjects must present to Visit 2 wearing the study lenses. To be counted as a day of wear the lenses need to have been worn for at least six (6) hours prior to the visit.

Visit 2: Treatment 1 Follow-up 1		
Step	Procedure	Details
2.1	Adverse Events and Concomitant Medications Review	Review the subject's concomitant medications and record any changes from the previous study visit.

Clinical Study Protocol
Johnson & Johnson Vision Care, Inc.

		Record any adverse events or medical history changes from the previous study visit.	
2.2	Wear time and Comfortable Wear time with Study lenses	Record the hours the subject has worn the study lenses and the comfortable wear time on the day of follow-up.	
2.3	Compliance	Record the subject's compliance with wearing the study lenses. Note: Subjects must have worn lenses for at least 6 hours per day To be counted as a day of wear at this visit the Subject must have worn the study lenses for 6 hours prior to the visit.	
2.4	CLUE Questionnaire	The subject will evaluate the vision characteristics, comfort characteristics, handling characteristics, and visual symptoms of the study lenses using the PRO questionnaire.	

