2.5	Ocular Symptoms	Subjects will respond to a verbal open-ended symptoms questionnaire.	
2.6	Subjective Acceptance	Record whether the subject's distance and near vision with the lenses is acceptable.	
2.7	Distance and Near Entrance Visual Acuity	Measure the distance and near visual acuity OD, OS and OU to the nearest letter. Record the results. For near measures use the ETDRS 2000 Series Chart 1 or 2. The acuity will be recorded to the nearest letter OD, OS and OU.	
2.8	Distance Over-Refraction and Distance Visual Acuity	Perform a distance over-refraction OD and OS using loose lenses outside of the phoropter under ambient room illumination. The distance over-refraction may also be refined under binocular conditions. Record the results and distance visual acuity OD and OS. The results of the distance over-refraction may also be checked for the impact on near vision under monocular and/or binocular conditions.	
2.9	Determination of Lens Optimization	If the subject reports unsatisfactory vision, or is unable to obtain 20/30 distance visual	

Clinical Study Protocol
Johnson & Johnson Vision Care, Inc.

		
acuity OU with the lenses then a modification must be attempted.
 
If the subject reports satisfactory vision with the lenses a modification is not required, however at the Investigator's discretion and based upon their findings on the measured visual acuity and/or over- refraction the investigator may make a modification.
 
Up to two attempts at modification are permitted if necessary, in order to achieve an acceptable distance and near binocular performance for the subject, and to enable them to wear that particular lens type.
 
Follow the fitting guide and steps 1.21-1.27 in Visit 1 Fitting allowing for at least 10 minutes of settling time between each lens modification.
	

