2.10	Lens Fit Assessment	
Evaluate and grade lens centration, primary gaze movement, upgaze movement and tightness (push-up test).
 
 • The subject should not proceed to wear the lenses if any of the following is observed: • presence of limbal exposure (appearance of clear cornea) in any gaze • presence of edge lift • presence of unacceptable movement (excessive or insufficient) in all three movement categories (primary gaze, upgaze, and push-up). 
If either lens is deemed unacceptable, the subject will be discontinued from the study. Remove the lenses, perform a slit-lamp evaluation, and complete the Final Evaluation form.
	
2.12	Lens Removal	The study lenses will be removed and discarded.	
2.13	Biomicroscopy	
Perform Biomicroscopy OD and OS. FDA Slit Lamp Classification Scales* will be used to grade the findings.
 
*note: for corneal staining note location (nasal, temporal, superior, inferior or central)
	

Clinical Study Protocol
Johnson & Johnson Vision Care, Inc.

		
If any of these slit lamp findings are Grade 3 or higher, an AE must be recorded. All AEs must be followed to resolution. After resolution the subject will be discontinued and Final evaluation completed.
 
If the clearance of the fluorescein needs to be expedited, preservative-free rewetting drops may be instilled.
	
2.14	Insertion of Study Lenses	Dispense the subject a new pair of lenses that match the distance and ADD power of the lenses that were removed in Step 2.12 above.	
2.15	PRO (MRD) Questionnaire	The subject will evaluate the vision characteristics, comfort characteristics, handling characteristics, and visual symptoms of the study lenses using the PRO questionnaire.	
2.16	Distance and Near Exit Visual Acuity	
Distance and near Snellen visual acuity will be measured for each eye with the study contact lenses in place.
 
For near measures use the ETDRS 2000 Series Chart 1 or 2.
 
The acuity will be recorded to the nearest letter OD, OS and OU.
 
Note: The distance visual acuity must be at least 20/30 OU for the lenses to be dispensed.
	
2.17	Dispensing Criteria	
The lenses will be dispensed for 10-14 days.
 
 • Distance Snellen acuity equal to or better than 20/30 OU • Subject must indicate that the vision is acceptable. • Subject must indicate that the comfort of the lenses is acceptable. • Lenses must have an acceptable general lens fit. 	

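### At Visit 2 the fit assessment follows lens optimization, so a lens replaced at step 2.9 gets no fit grade after its 2–4 days of wear

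*Protocol*

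**What the plan says.** **Endpoint.** Protocol 2.2 states: "Unacceptable lens fit will be assessed at all study visits (scheduled and unscheduled) for each subject eye". SAP 4 says the same, and both count an eye once however many unacceptable readings it has. Primary hypothesis 7 (Protocol 2.3, SAP 5.1) is that "the proportion (%) of eyes with an unacceptable fit during the study will be statistically less than 5" per cent.

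**Visit 2 (Protocol 7.2).** On arrival, "The subjects must present to Visit 2 wearing the study lenses". Entrance acuity (2.7) and over-refraction (2.8) come first, then optimization (2.9). A modification is required when vision is unsatisfactory or binocular distance acuity does not reach 20/30. Otherwise "If the subject reports satisfactory vision with the lenses a modification is not required", although the investigator may still make one. A modification is carried out thus: "Follow the fitting guide and steps 1.21-1.27 in Visit 1 Fitting allowing for at least 10 minutes of settling time between each lens modification". Up to two attempts are allowed. The lens fit assessment is 2.10, removal is 2.12 and biomicroscopy is 2.13. Step 2.14 then reads: "Dispense the subject a new pair of lenses that match the distance and ADD power of the lenses that were removed in Step 2.12".

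**Visit 1, for contrast.** Fit is graded at 1.27, ahead of modifications at 1.28: "If modifications are required steps 1.21-1.27 will be repeated for each modification".

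**The concern.** Visit 2 is the first chance to grade the fit of a lens that has been worn rather than just settled. As printed, an unmodified subject gets that grade at 2.10. A lens changed at 2.9 does not, because by 2.10 the eye carries a replacement that has settled for a minimum of 10 minutes. Whether the reading exists thus depends on a vision-driven decision taken earlier in the same visit.

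Unacceptable fit is a co-primary endpoint counted as ever or never per eye. An omitted reading can turn a recorded misfit into a non-event, but never the reverse. Any error therefore runs towards meeting the 5% target.

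**Working it through.** **1. Step order.** Steps 2.1–2.8 cover adverse events, wear time, compliance, the CLUE questionnaire, symptoms, acceptance, acuity and over-refraction. None grades fit. Step 2.9 follows 1.21–1.27: select, insert, settle, check vision, over-refract, grade fit. The 1.27 grade inside 2.9 therefore belongs to the new lens. Step 2.14 matches the new pair to the powers removed at 2.12, which makes sense only if the optimized powers were already on the eye by then.

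**2. Readings per eye, as printed.**

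| Reading | Lens replaced at 2.9 | Lens not replaced |
|---|---|---|
| Visit 1, step 1.27 | yes | yes |
| Visit 2, lens worn 2–4 days | **no** | yes (2.10) |
| Visit 2, replacement lens | yes (repeated 1.27, then 2.10) | not applicable |
| Visit 3, step 3.10 | yes | yes |

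Exactly one reading is missing.

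**3. Direction.** The eye-level outcome is 1 if any counted reading is unacceptable. Removing a reading can leave it unchanged or lower it.

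**4. Does the reading count?** SAP 4 and hypothesis 7 say yes. SAP 11.1 defines the fit proportion after two weeks of wear, and SAP 12.8 summarizes fit at fitting and at two weeks only. SAP 1 gives the SAP precedence over the protocol's statistical section, but that does not settle the matter, because the conflict lies within the SAP.

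**5. Scale of the fit test.** The step-order point rests on no stated figure, so this only shows how few eyes decide the test. Inputs:
- Eye-pair model (SAP 11.1), with Y the number of affected eyes: P(Y=0) = (1−ρ)(1−p)² + ρ(1−p); P(Y=1) = 2(1−ρ)p(1−p); P(Y=2) = (1−ρ)p² + ρp.
- Priors (SAP 14.2.1): p ~ Beta(0.5, 0.5), ρ ~ Uniform(0, 1).
- Borrowing (SAP Table 7): 23 + 66 = 89 subjects at a₀ = 0.3 and 86 at 0.1, worth 0.3×89 + 0.1×86 = 35.3 subjects.
- One historical unacceptable fit (SAP Table 6). Its platform is not stated, so both placements were run.
- Rule (SAP 11.1): pass if P(p<0.05) ≥ 0.975. N = 60.

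Posterior P(p<0.05) by numerical integration; ranges cover the platform placement and whether the affected eyes belong to one subject or several:

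| Affected eyes of 120 | With borrowing (primary) | Without (sensitivity) |
|---|---|---|
| 0 | above 0.999, pass | 0.9960, pass |
| 1 | 0.996–0.997, pass | 0.9751, bare pass |
| 2 | 0.988–0.990, pass | 0.925–0.941, fail |
| 3 | 0.969–0.974, fail | fail |

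The SAP code keeps 80,000/15 = 5,333 draws. If they were independent, the simulation error near the cut-off would be √(0.975×0.025/5,333) = 0.0021, so 0.9751 and 0.974 cannot be told reliably from 0.975.

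**6. Effect of missed readings (assumed range).** Let m be the share of truly misfitting eyes that only the missing reading would reveal. The recorded rate is then p(1−m). With borrowing, N = 60 and the planning correlation ρ = 0.80:

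| m | Pass if true rate 5% | Pass if true rate 1% |
|---|---|---|
| 0 | 13.9% | 85.2% |
| 5% | 16.0% | 86.4% |
| 10% | 18.3% | 87.5% |
| 20% | 23.8% | 89.7% |
| 30% | 30.7% | 91.8% |

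The 13.9% at m = 0 comes from the model with borrowing, not from step order. The plan states 90% power for fit. This model gives 85.2% at the planning rate, and 90.9% if the historical event is left out or a 0.95 rule is used. No error in the plan's power is claimed here.

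**The case against.** The best case for the plan is that little is lost.
- The replaced lens was graded at Visit 1 and had to fit acceptably to be dispensed. Its replacement is graded at Visit 2 and the final pair at Visit 3.
- All multifocal test lenses share one nominal base curve and diameter (Protocol Table 2), so a persistent misfit has further chances to be seen.
- Nothing says the step numbers are a compulsory order.
- If SAP 11.1 is read literally, no Visit 2 reading enters the test.

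The first two points stand: only a misfit visible solely on the worn lens at Visit 2 is lost. The third helps little, because the numbered steps are the only written sequence and 2.14 depends on it. If sites vary the order, some will grade the worn lens and others its replacement. The fourth is a genuine ambiguity, but SAP 4 contradicts it.

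A reader might infer more than the documents support:
- *Every modified subject loses the reading in both eyes.* Step 2.9 does not say that both lenses change, and the Appendix C insert describes a change to the non-dominant eye alone. An unchanged fellow lens would still be graded at 2.10.
- *Subjects with vision complaints misfit more often.* The triggers are vision and over-refraction. No passage links them to fit.
- *One missed eye decides the result.* Without borrowing, one affected eye still passes, if barely, and that is the sensitivity analysis. The primary analysis borrows and tolerates two.

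**Conclusion.** The step order leaves a real but narrow gap: a lens replaced at 2.9 has no fit grade after 2–4 days of wear, whereas an unreplaced lens has one. Under the all-visits definition the gap can only reduce the number of unacceptable fits.

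Its size cannot be derived from the documents. The modification rate and the share of misfits seen only at that reading are both absent, and the values of m above are assumptions. What can be said is that the primary fit verdict changes between two and three affected eyes of 120, assuming 60 subjects. The safety population may be larger, since 80 are to be enrolled. It would be too strong to say that the affected eyes go ungraded, that the co-primary certainly loses data, or that the trial would pass wrongly. The eyes keep their other grades, and SAP 11.1 leaves open whether any Visit 2 reading counts.

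**What to change.** 1. In Protocol 7.2, have the fit of the worn lenses graded and recorded before any lens change at 2.9. Rely on the repeat of 1.27 within 2.9 for each modified lens.
2. Step 2.10 also carries discontinuation text. The sponsor should reconcile how that text applies to a worn-lens grade taken ahead of optimization. This point concerns only when the grade is recorded and proposes no clinical rule.
3. Reconcile SAP 4 and hypothesis 7 (every visit, throughout the study) with SAP 11.1 (after two weeks) and SAP 12.8 (fitting and two weeks), and state which fit readings enter the endpoint, including both the worn-lens and replacement-lens grades at Visit 2 if all visits count.

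The cost is a reordering of existing steps in the protocol and eCRF, the reconciliation in item 2, and a short SAP clarification. The worn-lens grade moves forward from 2.10, and replacements are already graded at the repeated 1.27, so no new type of assessment is needed.

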7.3. Unscheduled Visits

If, during the investigation, a subject requires an unscheduled visit to the clinical site, the following information will be collected at a minimum:

- Chief complaint prompting the visit. If the reason is an adverse event, the applicable eCRF for the adverse event must be completed and subject record completed as appropriate.
- Date and time of the visit and all procedures completed at the unscheduled visit.
- Review of adverse event and concomitant medications.
- Documentation of any test article dispensed or collected from the subject, if applicable.
- Slit lamp findings (using the Slit Lamp Classification Scale).

If the Investigator withdraws a subject from the study, the final study visit case report forms must be completed indicating the reason(s) why the subject was withdrawn. The subject record

Clinical Study Protocol
Johnson & Johnson Vision Care, Inc.

must be completed documenting the date and primary reason for withdrawal and the study CRA notified.

Any ocular and non-ocular Adverse Events that are ongoing at the time of the study visit will be followed by the Investigator, within licensure, until they have resolved, returned to pre-treatment status, stabilized, or been satisfactorily explained. If further treatment i.e., beyond licensure is required, the subject will be referred to the appropriate health care provider.

The following information will be collected during an unscheduled visit.

Unscheduled Visit		
Step	Procedure	Details
U.1	Chief Complaints	Record the subject's chief complaints for reasons for the unscheduled visit
U.2	Adverse Events and Concomitant Medications Review	Review the subject's concomitant medications and record any changes from the previous study visit.
U.3	Subject Reported Ocular Symptoms	Subjects will respond to a verbal open-ended symptoms questionnaire.
U.4	Entrance VA	Record the entrance distance and near visual acuity (OD, OS and OU). For near measures use the ETDRS 2000 Series Chart 1 or 2. The acuity will be recorded to the nearest letter OD, OS and OU.
U.5	Subjective Sphero-cylindrical Refraction	An optimal, binocular balanced distance sphero-cylindrical refraction will be performed. Record the refraction and distance visual acuity to the nearest letter.
U.6	Biomicroscopy	FDA Slit Lamp Classification Scale* will be used to grade the findings. *note: for corneal staining note location (nasal, temporal, superior, inferior or central) If any of these slit lamp findings are Grade 3 or higher, an AE must be recorded. All AEs must be followed to resolution. After resolution the subject will be discontinued and Final evaluation completed If the clearance of the fluorescein needs to be expedited, preservative-free rewetting drops may be instilled.

Clinical Study Protocol
Johnson & Johnson Vision Care, Inc.

Unscheduled Visit			
U.7	Lens Dispensing	Additional study lenses may be dispensed when required.	
U.8	Lens Fit Assessment:	
Evaluate and grade lens centration, primary gaze movement, upgaze movement and tightness (push-up test).
 
The subject should not proceed to wear the lenses if any of the following is observed:
 
 • presence of limbal exposure (appearance of clear cornea) in any gaze • presence of edge lift • presence of unacceptable movement (excessive or insufficient) in all three movement categories (primary gaze, upgaze, and push-up). 
If either lens is deemed unacceptable, the subject will be discontinued from the study. Remove the lenses, perform a slit-lamp evaluation, and complete the Final Evaluation form.
	
U.9	Exit Visual Acuity	
Record the subject's exit distance and near visual acuity (OD, OS and OU).
 
For near measures use the ETDRS 2000 Series Chart 1 or 2.
 
The acuity will be recorded to the nearest letter OD, OS and OU.
	

